# Remote glucose monitoring using the Dexcom G6 Continuous Glucose Monitoring (CGM) System in hospitalized patients with diabetic ketoacidosis (DKA)

Study Purpose and Rationale:

We propose to study use of Continuous Glucose Monitoring (CGM)for glucose monitoring in patients with DKA which would enable the treatment of hemodynamically stable DKA patients outside of intensive care units (ICU) thereby saving ICU beds a precious resource which have become extremely scarce resource during COVID-19 pandemic (1). In most hospitals, protocols for treatment of patients with diabetic ketoacidosis (DKA) require capillary point of care (POC) glucose testing every 1-2 hours (2) . Often, patients need to be transferred to the intensive care units (ICU) for frequent fingerstick glucose monitoring in order to safely administer intravenous insulin to treat the DKA. During the COVID-19 pandemic, this need to transfer patients to the intensive care unit (ICU) for treatment of DKA and the requirement for nurses to enter the room every 1-2 hours has contributed to scarcity of critical care unit beds and shortage personal protective equipment (PPE) Additionally, COVID-19 patients have been prone to develop DKA which has further increased the need for ICU beds (3, 4). Therefore, methods to safely and effective treat patients with DKA outside of ICU setting represent a common and pressing need.

Continuous glucose monitoring (CGM) is widely used in the outpatient setting but its use is still investigational in the inpatient setting. Several studies showed improvement in detection of hyperglycemic and hypoglycemic episodes with the use of CGM when compared to fingerstick point of care (POC) glucose testing in both the ICU and non-ICU setting (5-8). The FDA has allowed use of DEXCOM G6 CGM in hospitalized patients during the COVID-19 pandemic (9). In a recent pilot study performed during the COVID-19 pandemic done in hospitalized patients in the perioperative period, DEXCOM G6 CGM showed a mean absolute relative difference (MARD) of 9.4% compared to point of care (POC) glucose measurements (10). Use of continuous glucose monitoring has not been reported in hospitalized patients with DKA. The DEXCOM G6 CGM (https://www.DEXCOM G6.com/) provides glucose levels in real time, as well as glucose trends, and alarms if glucose levels are in hypoglycemic or hyperglycemic range. These safety features can decrease the risk of hypoglycemia when patients with DKA are being treated with insulin infusion. Furthermore, the DEXCOM G6 CGM is labeled as an "integrated continuous glucose monitoring system" which can reliably and securely transmit glucose data to digital devices allowing remote monitoring of glucose levels by multiple care team members without entering patient's room and thus reducing the number of healthcare contact and use of personal protective equipment (PPE). If CGM is shown to be non-inferior to fingerstick glucose monitoring (measured by time to resolve DKA, incidence of hypoglycemia) in patients with DKA, then hemodynamically stable non-intubated DKA patients would not have to be transferred to the ICU for frequent fingerstick glucose testing as is now being done. Instead, these patients could be treated and monitored with CGM on the stepdown unit. This would help reallocate critical care unit beds, save time and effort for the nurses and help conserve PPE.

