#### **Prospective Study**

The prospective part of this study will involve recruiting patients in the Emergency Department and offering them the opportunity to use DEXCOM G6 CGM instead of hourly fingerstick point of care glucose testing . We will enroll additional 50 non-critically ill DKA patients who will have glucose levels monitored via DEXCOM CGM and be treated in the stepdown unit. The primary outcome is time to resolution of metabolic acidosis. Secondary outcomes are length of ICU stay, length of hospital stay, frequency of hypoglycemic episodes defined as glucose level <70 mg/dl and cost savings.

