# Statistical Procedures:

The primary outcome for this study is the time to resolution of DKA. We will compare time to resolution of the DKA of patients who had glucose levels monitored via DEXCOM G6 CGM and treated in the stepdown unit (both those enrolled in the retrospective study and those who will be enrolled in the prospective study) to DKA patients who had glucose levels monitored hourly via fingerstick (and not CGM) and treated in the ICU setting.

We will perform a non-inferiority trial to study whether monitoring glucose levels via CGM in DKA patients treated in the stepdown unit is not inferior to DKA treated patients in the ICU setting with hourly fingerstick glucose monitoring.

For a noninferiority trial, based on what we have previously observed for the time to resolution of DKA, and a noninferiority margin of 1/2 the SD, we estimate that a sample size of 98 patients per group will have a 90% power to determine noninferiority at an alpha level of 0.05. Since we enrolled 48 patients in the retrospective part of the study, we will need additional 50 patients enrolled in the prospective part of the study to have 90% power and a noninferiority at an alpha level of 0.05. We plan a conservative approach where we will enroll additional 50 DKA patients who will have glucose levels monitored via CGM. We will compare with the historical control using 1:1 matching, thus will collect historical control data which include DKA patients treated for DKA in the ICU setting with hourly fingerstick glucose monitoring.

We will perform linear regression (for patients enrolled in both retrospective and prospective part of the study) to learn what clinical factors are associated with length of time to the DKA resolution. Then we will use propensity matching for historical control group (DKA patients treated in the ICU setting with glucose levels monitored via hourly fingerstick glucose levels).

To study the frequency of hypoglycemic episodes (<70 mg/dl) in patients from both prospective and retrospective study; we will use CGM glucose data stored manufacture's web based software : Clarity.

We will also evaluate frequency of hypoglycemic episodes (glucose level <70%) in historical control patients who were treated for DKA in the ICU and had hourly glucose level monitoring.

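### The rationale's practice conclusion needs non-inferiority on hypoglycemia as well as time to resolution, but the plan designs that test for time only and measures hypoglycemia differently in the two groups

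*Combined protocol and SAP*

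**What the plan says.** The combined protocol and SAP treats hypoglycemia in three ways.

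- **Study Purpose and Rationale** sets the condition under which stable patients could be managed on the stepdown unit: "If CGM is shown to be non-inferior to fingerstick glucose monitoring (measured by time to resolve DKA, incidence of hypoglycemia". Both measures sit inside that condition.
- **Study Design** (retrospective and prospective parts) makes time to resolution of acidosis the primary outcome. Among the secondary outcomes it lists "frequency of hypoglycemic episodes defined as glucose level <70 mg/dl".
- **Statistical Procedures** repeats that "The primary outcome for this study is the time to resolution of DKA". The sample size of 98 per group (90% power, alpha 0.05) is "based on what we have previously observed for the time to resolution of DKA, and a noninferiority margin of 1/2 the SD". For hypoglycemia the section names data sources only: the manufacturer's stored CGM record for the CGM patients and, for the comparison group, "We will also evaluate frequency of hypoglycemic episodes (glucose level <70%) in historical control patients", who were monitored hourly by fingerstick. It gives no expected rate, margin, test, confidence interval or rule for combining the two measures.

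**The concern.** Hypoglycemia is the natural safety question when an insulin infusion is run outside the ICU with CGM-guided adjustment. Potential Risks names it as a consequence of inaccurate device readings, and Data and Safety Monitoring covers only data storage. The between-group hypoglycemia comparison is therefore the main comparative safety evidence the study will produce.

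Two things limit that evidence. First, the design has no non-inferiority framework for hypoglycemia, although the rationale's conclusion calls for one. Without a stated rule, a reader of the results could take the absence of a significant difference as meeting the rationale's condition. Second, the groups are observed differently: a continuous record on one side, one reading an hour on the other. A difference, or its absence, would then mix the effect of care with the effect of measurement.

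**Working it through.** **1. The plan's own figure.** Inputs from Statistical Procedures: margin 0.5 SD, 90% power, alpha 0.05 (sidedness not stated). Assuming no true difference and independent groups, n per group = 2(z_alpha + z_power)² / 0.5².

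- One-sided 0.05: 8 × (1.645 + 1.282)² = 68.5, so 69.
- One-sided 0.025: 8 × (1.960 + 1.282)² = 84.1, so 85.

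Neither gives 98, so some unstated adjustment was probably made. It errs on the high side. Power for time at 98 per group is Φ(0.5 × √(98/2) − z) = Φ(3.5 − 1.960) = 93.8%, or Φ(3.5 − 1.645) = 96.8%. Sample size for time is not the weak point.

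**2. Precision for hypoglycemia.** The documents give no rate. I assume the same true proportion p of patients with an event in each group, at 5%, 10% or 20%, and independent groups of 98. SE = √(2p(1−p)/98) = 3.11, 4.29 or 5.71 points. The 95% half-width, 1.96 × SE, is 6.1, 8.4 or 11.2 points.

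**3. Power against assumed margins.** Power = Φ(m/SE − z), with m = 5 or 10 points (also assumed). Both alpha conventions are shown because the plan does not choose one.

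| Margin, test | p = 5% | p = 10% | p = 20% |
|---|---|---|---|
| 5 points, one-sided 0.025 | 36% | 21% | 14% |
| 5 points, one-sided 0.05 | 48% | 32% | 22% |
| 10 points, one-sided 0.025 | 89% | 65% | 42% |
| 10 points, one-sided 0.025, exact score test | 82% | 61% | 41% |
| 10 points, one-sided 0.05 | 94% | 75% | 54% |

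Example: p = 10%, m = 10 gives 10/4.29 − 1.960 = 0.373, and Φ(0.373) = 65%.

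**4. Margin that 98 per group could support.** For 90% power at one-sided 0.025, m = 3.242 × SE = 10.1, 13.9 or 18.5 points. At one-sided 0.05 it is 9.1, 12.5 or 16.7 points. At a 5% rate, a 10-point margin would accept 15%, a tripling.

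**5. Effect of unequal detection.** Suppose, as an illustration, that the true rates are equal but the CGM record shows events in 10% of patients and fingersticks in 5%. SE = √((0.10 × 0.90 + 0.05 × 0.95)/98) = 3.75 points. Power at a 10-point margin is Φ((10 − 5)/3.75 − 1.960) = 27%, against 89% when both groups record 5%.

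**The case against.** The strongest reply is that the sentence in the rationale is background, a conditional remark about what might follow for practice. The operative sections agree with each other: one primary outcome, with hypoglycemia secondary. A descriptive secondary outcome needs neither a margin nor power. That stands. It is why the remedy is to narrow the claim and not to enlarge the trial.

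Several stronger readings are tempting and should not be drawn:

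- *That the plan will claim equal safety from a non-significant result.* No section specifies a significance test for hypoglycemia or says how its result will be interpreted. The plan leaves room for that reading but does not state it.
- *That 98 per group could work only if events were rare and the margin wide.* A wide margin alone is enough: at one-sided 0.025, 15 points at a 10% rate and 20 points at a 20% rate each give 94% power.
- *That incidence in the rationale and frequency elsewhere are proven to be two different measures.* Incidence can also mean events. The wording is loose and needs settling, no more.
- *That the percent sign after 70 in Statistical Procedures is a second threshold.* The paragraph before it uses mg/dl, so this is a slip.

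It is also fair to say that the rates and margins above are mine, and that the planned 1:1 matching could shift the figures modestly.

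**Conclusion.** The point holds as a mismatch between the conclusion foreseen in the rationale and what the design can deliver. Time to resolution has a margin and ample numbers. Hypoglycemia has no margin and no common measurement, so the plan as written cannot support the second half of the rationale's condition.

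The size of the shortfall depends on the event rate, which the documents do not give. Over assumed rates of 5% to 20%, power for a 5-point margin stays below 50% under either alpha convention. For a 10-point margin it runs from 42% to 89% at one-sided 0.025 and from 54% to 94% at one-sided 0.05. The direction of the detection bias, probably against CGM, is inferred from the rationale's own statement about CGM and from the two monitoring schedules. Its size cannot be derived from the documents.

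**What to change.** 1. In Study Purpose and Rationale, limit the non-inferiority claim to time to resolution.
2. In Statistical Procedures, say that hypoglycemia (<70 mg/dl) will be reported as a between-group difference with a 95% confidence interval beside the primary result. Add that a non-significant difference will not be read as non-inferiority or equal safety.
3. Base that comparison on a common measure. One option is CGM values sampled hourly to match the control fingerstick schedule. Another is fingerstick-confirmed events where recorded. The second would miss lows at which the CGM did not prompt a fingerstick, so its bias could run the other way. Report the full CGM record separately as descriptive, and state any remaining detection difference as a limitation.
4. Choose one measure, for example patients with at least one episode, and use it in the rationale, both parts of Study Design and Statistical Procedures. Correct the unit slip at the same time.

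No additional patients are needed. The cost is a safety statement weaker than the rationale now implies, and a small amount of extra data handling and analysis for the common measure.

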### Study Design:

#### Retrospective Quality Improvement Data

In January 2021 during COVID 19 pandemic, we launched a quality improvement project with goal to treat non-critically ill DKA patients outside of ICU setting in order to reallocate ICU beds for critically ill patients at New York Presbyterian Hospital /Columbia University Irving Medical Center. Before this quality improvement project, DKA patients were treated in the ICU setting because the DKA protocol requires hourly fingerstick glucose monitoring, which is considered higher level of care and not appropriate for stepdown unit or medical/surgical wards. During this quality improvement project, we monitored glucose levels remotely with continuous glucose monitoring (CGM) device DEXCOM G6 thus eliminating the need for hourly fingerstick glucose testing. Therefore, patients with DKA whose glucose levels have been monitored via DEXCOM G6 CGM have been treated in the stepdown unit instead of the ICU setting where glucose levels are monitoring hourly via fingerstick point of care glucose testing. We enrolled 48 patients (with additional 2 patients who had glucose levels monitored with CGM but were treated in the ICU setting therefore will not be used for this analysis).

Study participants were not being recruited and asked for their participation; non-critically ill DKA patients who presented in DKA had glucose levels monitored via CGM. Given that the recommended hourly fingerstick checks needed for treatment could not be performed on the stepdown unit and only in the ICU, the Dexcom G6 CGM device eliminated the need for hourly fingerstick checks and thus removed the barrier for patients being admitted to stepdown. Once the number of COVID cases decreased and ICU beds were more readily available, the hospital returned to practicing the pre-COVID standard of care, which was admitting DKA patient to the ICU for hourly glucose monitoring and we stopped enrolling patients for this retrospective quality improvement project

We propose to study outcomes of DKA patients who had glucose levels monitored with DEXCOM G6 CGM treated in the stepdown unit. The primary outcome is time to resolution of metabolic acidosis. Secondary outcomes are length of ICU stay, length of hospital stay, frequency of hypoglycemic episodes defined as glucose level <70 mg/dl and cost savings

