# Exclusion criteria:

hypotension (BP below 80/60), require pressor therapy, or have any contraindication for utilizing Dexcom CGM ,, altered mental status, lack of decision making capacity, mechanical ventilation or non-invasive ventilation, chronic kidney disease with GFR <30 including patients with hemodialysis, pregnancy, other clinical reason for admission to the intensive care unit (ICU) , are excluded from study participation

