#### Prospective Study

Patients who have glucose levels monitored by the CGM will be treated in the Stepdown Unit instead of intensive care unit (ICU) setting. Glucose levels from the CGM will be transmitted to the smartphones devices which will be provided to the provider and nurse taking care of the patient by the study team.

We provided extensive training for the ED staff and Stepdown Unit staff regarding the use of CGM in patients with DKA. Additionally, we will provide information sheet describing provider and nurses' role when DKA patients are monitored via CGM.

Once provider and the nurse in the ED give verbal consent for the study, and patient gives a written consent, a research coordinator will attach CGM DEXCOM G6 device (which consists of sensor and transmitter) on patient's arm and set up smartphone devices (study patient smartphone, study provider smartphone and study nurse smartphone) to receive glucose levels from the CGM device.

Description of the remote glucose monitoring via CGM device and workflow:

1. A research coordinator will apply sensor (which senses glucose levels just below the skin from the interstitial fluid) and transmitter (which gets glucose information from the sensor and send glucose information to the DEXCOM G6 app via Bluetooth to the smart phone provided by the study team) on the patient. The Dexcom CGM will be attached to the upper arm or lower abdomen. The patient will be asked for their preference. The Dexcom CGM should not be placed where the patient is lying down or sleeps. CGM will not be placed on scars, hair, tattoos, irritated areas, areas where the sensor can be rubbed (waist band, seat belt), and insulin injection sites. The patient may already be wearing their own personal CGM, which should not be removed. If the patient's personal CGM is on the arm, the study Dexcom CGM will be attached to the lower abdomen. If the patient's upper arm. The study patient smartphone receiving glucose level data needs to be placed on the patient's IV pole next to the insulin bag.

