- 3. Once glucose levels are transmitted to the study smartphone devices, glucose levels from the CGM to guide insulin adjustments. Check fingerstick glucose if CGM glucose levels are <100 mg/dl and >350 mg/dl to guide treatment decisions. Note that CGM device will have audible alerts if glucose level are < 100 mg/dl and >350 mg/dl. If there are NO glucose levels transmitted to the phone please check q 1 fingerstick glucose levels and contact [name] ([name]). If CGM glucose data cannot restored and patient needs g 1 hour fingerstick glucose testing, patient will be transferred to the ICU. If patient is moved to the ICU the CGM will be removed. Although CGM data will be transmitted to the study smartphone devices continuously, please monitor CGM glucose levels every 1 hour and make treatment decisions based on q 1-hour CGM readings or more frequently when glucose levels are <70 mg/dl (confirmed with a fingerstick glucose). If patient's glucose levels are <100 mg/dl on the CGM, fingerstick glucose testing will be performed to ensure that fingerstick glucose level is not in hypoglycemic range (<70 mg/dl). If patient's glucose levels are in hypoglycemic range (<70 mg/dl), fingerstick glucose levels testing will be performed as per hospital protocol until hypoglycemia resolves. Once hypoglycemia resolves, then glucose levels from the CGM can be used for further insulin adjustments. In the Emergency Department, document glucose levels q 2 hours as per the research protocol or more frequently as per provider request treating the patient. When patient is transferred to the stepdown unit, glucose levels should be recorded every 3 hours in hospital electronic medical record system.
- 4. If the patient condition worsens and patient requires the ICU care, patient will be transferred to the ICU. Also, if patient needs to get MRI or CT, sensor and transmitter will be removed prior to the imaging.
- 5. Smartphones which are receiving glucose data (study provider smart phone, study nurse smart phone and the study patient smart phone which receives glucose level from the sensor and is next to the IV insulin bag) should be transferred to the Stepdown Unit nurse when patient is arrives at the Stepdown Unit.

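### Two CGM-monitored retrospective patients are left out because they were treated in the ICU, and the plan does not say whether later ICU transfers stay in the CGM group (minor; cheap to settle)

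*Combined protocol and SAP*

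**What the plan says.** **The two patients.** Study Design, Retrospective Quality Improvement Data, reports 48 enrolled patients and mentions "additional 2 patients who had glucose levels monitored with CGM but were treated in the ICU setting therefore will not be used for this analysis". No eligibility criterion is cited and no timing is given. The Exclusion criteria do bar patients who have another clinical reason for ICU admission, but the text does not link the two patients to that criterion.

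**The CGM group.** Statistical Procedures describes it as "patients who had glucose levels monitored via DEXCOM G6 CGM and treated in the stepdown unit", then adds in parentheses "both those enrolled in the retrospective study and those who will be enrolled in the prospective study". The count is 48 retrospective plus 50 prospective patients, 98 in all.

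**The control group.** Controls are historical, matched 1:1 and selected as "DKA patients treated for DKA in the ICU setting with hourly fingerstick glucose monitoring".

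**Routes to the ICU after CGM has started.** In Study Procedures, Prospective Study, CGM begins in the emergency department. Item 3 covers signal failure: "If CGM glucose data cannot restored and patient needs g 1 hour fingerstick glucose testing, patient will be transferred to the ICU". Item 4 covers deterioration: "If the patient condition worsens and patient requires the ICU care, patient will be transferred to the ICU". Neither item says how such a patient is analysed, and the document defines no analysis set.

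**Hypoglycaemia data.** Statistical Procedures takes CGM-group hypoglycaemia from the manufacturer's Clarity software. Items 3 and 4 have the device taken off on transfer to the ICU and before MRI or CT.

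**The concern.** Where a patient is treated can be a consequence of how the patient fares, and length of ICU stay is itself a secondary outcome. A group limited to patients treated in the stepdown unit may therefore leave out those for whom the strategy did not work. The comparison then concerns patients for whom stepdown care with CGM succeeded, not patients started on it.

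The rule cannot act equally on both sides. ICU treatment is a condition for being a control, so it never removes one. Matching may drop controls, but on patient characteristics, not on care setting.

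Three results could be affected: the primary comparison of time to resolution, the ICU-day and cost comparisons (a stepdown-only group has few ICU days almost by construction), and the hypoglycaemia count, where the named source stops when the sensor comes off.

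**Working it through.** **1. Counts.** 48 + 50 = 98, which agrees with the plan's CGM total. With the two added, 48 + 2 = 50 retrospective patients and 50 + 50 = 100 started on CGM. The two are 2/50 = 4.0% of the retrospective CGM-monitored patients and 2/100 = 2% of the pooled group.

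**2. The plan's sample size.** With margin 0.5 SD, true difference 0 and 90% power, n = 2(z_alpha + 1.282)²/0.5². This gives 69 per group at one-sided 0.05 and 85 at one-sided 0.025, not the stated 98. Since 98 exceeds both, there is no shortfall, and this point does not depend on it. The plan does not state the sidedness of alpha, so both are shown below.

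**3. Shift from omitting the two.** Let k be the mean excess time to resolution, in SD, of the two over the other 98 CGM patients, beyond what matching explains. The documents do not give k, so it is assumed.

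Mean of all 100 = mean of the 98 + (2/100)k, so omission lowers the CGM mean by 0.02k SD. As a share of the margin this is 0.02k/0.5 = 4% per unit of k.

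**4. False non-inferiority.** Suppose the true difference among all started patients equals the 0.5 SD margin. Treat the groups as independent with a common SD: SE = sqrt(1/98 + 1/98) = 0.1429. The probability of wrongly declaring non-inferiority is Phi(0.02k/0.1429 − z), with z = 1.960 or 1.645.

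| Assumed k (SD) | Shift (SD) | Share of margin | One-sided 0.025 | One-sided 0.05 |
|---|---|---|---|---|
| −1 | −0.02 | −4% | Phi(−2.100) = 0.018 | Phi(−1.785) = 0.037 |
| 0 | 0 | 0% | 0.025 | 0.050 |
| 1 | 0.02 | 4% | Phi(−1.820) = 0.034 | Phi(−1.505) = 0.066 |
| 2 | 0.04 | 8% | Phi(−1.680) = 0.0465 | Phi(−1.365) = 0.086 |
| 3 | 0.06 | 12% | Phi(−1.540) = 0.062 | Phi(−1.225) = 0.110 |

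Simulation (40,000 trials per value of k from 0 to 3) agrees: 0.024, 0.036, 0.046 and 0.062 at one-sided 0.025. Keeping all 100 against 100 controls gives 0.020 to 0.026.

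**5. ICU days.** If each of the two stayed L days in the ICU, omission removes 2L/100 days per CGM-started patient: 0.02 at an assumed L = 1, and 0.10 at L = 5.

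**6. Power with all kept (true difference 0, one-sided 0.025).** Phi(0.5/sqrt(2/98) − 1.960) = 93.8%; Phi(0.5/sqrt(2/100) − 1.960) = 94.2%.

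**7. Prospective transfers.** The documents give no number. By the same formula, each patient removed from a total of 100 adds 0.01 SD of shift per SD of excess.

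**8. Hypoglycaemia source.** Clarity holds sensor data only. Events after removal under items 3 and 4 are therefore outside the named source. Chart abstraction is planned for the prospective patients, but fingerstick values are not named as a hypoglycaemia source for the CGM group.

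**The case against.** The plan compares one package, CGM with stepdown care, against another, fingerstick testing with ICU care. If the two were in the ICU from the start, they never received the package, and leaving them out is a matter of eligibility. The text counts them outside the 48 enrolled and openly gives their number and the reason. It mentions no transfer. The prospective workflow removes the device on transfer to the ICU, so CGM monitoring together with ICU treatment fits direct ICU admission at least as well as a rescue. This stands: their route is unknown.

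A reader might infer that prospective patients moved to the ICU will be dropped. The documents do not say so. The enrolment wording, the use of all 50 to reach 98, and ICU stay as an outcome for these patients all favour keeping them. What remains is that no passage settles it, while the stepdown wording and the handling of the two point the other way. Large distortions reached by supposing 5 or 10 prospective removals have no documentary basis and carry no weight here.

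A reader might also infer that the exclusion necessarily flatters CGM. That is not shown. Only the removal is one-sided; the sign of any bias depends on how the omitted patients fared.

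Nor is the all-started set plainly the conservative one. Counting ICU care after transfer can make the groups more alike, which can itself favour non-inferiority. This also stands, and it is a reason to report both sets.

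Finally, the Clarity gap is a separate matter. It is limited mainly to ICU transfers and imaging, because item 6 otherwise keeps the sensor on until ward transfer or 10 days. It does not raise the severity of the main point.

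**Conclusion.** The point holds as a minor one. The plan leaves out two CGM-monitored patients on care location alone, repeats the stepdown condition in the primary comparison, and gives no rule for later ICU transfers. Location can act on the CGM side only.

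For the two alone the effect is small: 0.02 SD per SD of assumed excess. At one-sided 0.025, false non-inferiority at the margin goes from 2.5% to 3.4% at 1 SD and about 4.6% at 2 SD. These figures assume a true difference exactly at the margin and an excess that matching does not explain; neither is documented. With no excess the primary outcome is unbiased, and with a negative one the bias reverses. That the two were failures of stepdown care is not established. The effect of prospective transfers cannot be sized from the documents.

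The hypoglycaemia gap is real on the text, but no size can be given for it.

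**What to change.** 1. State in the SAP that every eligible patient started on CGM with stepdown care intended, retrospective or prospective, stays in the CGM group after signal loss, sensor removal or ICU transfer. Count time to resolution, ICU days, cost and hypoglycaemia after transfer.
2. Review the charts of the two retrospective patients and state why they were in the ICU. Report the primary result with and without them, unless they were ineligible or ICU care was planned from the start.
3. Take hypoglycaemia after sensor removal from fingerstick values in the medical record, and name that source.
4. Report the number of ICU transfers with reasons, and give the set treated in the stepdown unit throughout as a sensitivity analysis.

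**Cost.** SAP wording, two chart reviews, and up to 2 more matched controls (100 instead of 98). Power is essentially unchanged. Intended care may be hard to recover for the two, which is why the result is reported both ways. The CGM result may look less favourable.
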